2.2.2 Nonclinical Pharmacokinetics

After a single intravenous dose of 10mg/kg surufatinib in rats, the plasma elimination half-life of surufatinib was measured as 2.8 hours, and plasma clearance and apparent volume of distribution were 3.53 L/h/kg and 13.1 L/kg, respectively. Following dosing via oral gavage at low, medium and high dose levels, the mean value of time to reach maximum concentration was 3.0~4.2 hours. The oral bioavailability was observed to be dose dependent. At the dose level of 10 mg/kg, the bioavailability was just 9.9%. When the dose was increased to 40 mg/ml or above, the bioavailability exceeded 50%. The low bioavailability observed at the low dose level might be associated with the efflux by P-glycoprotein in intestinal epithelial cells.

After a single intravenous dose of 5 mg/kg in dogs, the plasma elimination half-life was 3.3 hours, and plasma clearance and apparent volume of distribution were 3.94 L/h/kg and 18.5 L/kg, respectively. Following a single oral dose of 5, 10 and 20 mg/kg, the mean value of time to reach maximum concentration was 3.5~4.5 hours. In the dose range of 5~20 mg/kg, surufatinib exposure (C_{max} and AUC_{0-t}) increased dose-proportionally. Feeding had no obvious effect on the extent and speed of surufatinib absorption. At the oral dose level of 10 mg/kg, the absolute bioavailability was 30.5%.

After administration via oral gavage in rats, surufatinib was distributed widely in various tissues mainly including lung, liver, spleen, adrenal gland, kidney, pancreas and stomach wall. The lowest drug concentration was observed in brain, indicating poor brain blood penetration. At 24 hours post-dose, concentrations in most tissues reduced to 10% or lower than the peak concentrations.

The results of [14C]-surufatinib excretion study revealed that surufatinib was mostly excreted via faeces (approximately 80% of the dose, including 40% for bile excretion), and a small amount was excreted via urine (approximately 10% of the dose).

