4.1.4 Secondary Endpoints

The secondary endpoints of the study include the primary PK parameters and the treatment outcomes (per RECIST Version 1.1) as described below.

- Pharmacokinetic parameters, which include:
 - Maximum plasma concentration (C_{max})
 - Time to reach maximum concentration (T_{max})
 - Terminal half-life ($t_{1/2}$)
 - Area under the concentration-time curve in a selected time interval (AUC_{0-t})
 - Area under the concentration-time curve in the time interval from 0 to infinity ($AUC_{0-\infty}$)
 - Apparent clearance (CL/F)
 - Apparent volume of distribution (V_z/F)
 - Mean residence time (MRT)
 - Accumulation index based on AUC
- ORR
- DCR
- DoR
- PFS
- Percentage change in tumor size from baseline according to RECIST Version 1.1

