4.2 Dose Expansion Phase

4.2.1 Primary Objective

To evaluate the anticancer activity of surufatinib at the recommended phase 2 dose (RP2D) from the dose escalation phase, in patients with advanced BTC, patients with advanced pNETs, patients with locally advanced, unresectable, metastatic epNETs, and patients with STS treated at a dose of 300 mg QD .

NOTE: The MTD/RP2D of 300 mg QD was declared at the time Amendment 7 was written. The RP2D in this trial is the same as the RP2D used in clinical trials in China.

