4.2.4 Secondary Endpoints

- Pharmacokinetic parameters, which include but are not limited to, C_{max} , T_{max} , first-order rate constant K_{el} , AUC, $t_{1/2}$, CL/F , V_z/F , accumulation ratio, and dose proportionality between AUC and dose and C_{max} and dose
- Safety, as assessed by:
 - The frequency and severity of adverse events
 - Physical examination findings
 - Vital signs
 - Laboratory test results (ie, hematology, chemistry panel, and urinalysis)
 - 12-lead electrocardiogram
 - Echocardiogram
- Efficacy treatment outcomes, which consist of:
 - ORR
 - DCR
 - TTR
 - DoR
 - Percentage change in tumor size from baseline (per RECIST Version 1.1)

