Patients who complete the DLT observation window (Cycle 1, Day 1-28) and are deemed, in the investigator's judgment, to have benefited from surufatinib treatment could be permitted, at the investigator's discretion, to continue with surufatinib treatment until disease progression, death, intolerable toxicity, pregnancy, or loss of benefit from the study drug. Patients with acceptable toxicity and ongoing clinical benefit were to be permitted to receive surufatinib for up to 1 year at the investigator's discretion and with the sponsor's agreement. Intra-patient dose escalation to a higher dose that has been cleared (ie, no DLT

in 3 patients or 1 or less DLT in at least 6 patients) was to be allowed if the sponsor and investigator both agreed.

Please see the flowchart for dose escalation in Table 3 and [Section 7.2](#) for dose modification instructions.

Table 3 Flowchart of Dose Escalation

Cohort	Dose	Patients	DLTs/patients	Dose Escalation Decision
1	50 mg QD	3-6	0/3	Escalate to 100 mg QD
			1/3	Enroll 3 additional patients
			1/3+0/3	Escalate to 100 mg QD
			1/3+1/3 or 2/3 or 3/3	Stop dose escalation
2 (or 3, 4, etc.)	100 mg QD or higher	3-6 per cohort	Follow the same rules as above	

An improved surufatinib formulation in 50 mg and 200 mg capsules (formulation No. PD-012-042) was introduced while the dose escalation phase of the study was ongoing. The improved surufatinib capsules have replaced the older surufatinib capsules (formulation No. PD-012-023), and will be used for the rest of the trial. Improved formulation (PD-012-042) showed improved consistency of production capability compared to the prior formulation (PD-012-023), including content uniformity with comparable quality attributes. The dose escalation of the new surufatinib capsules will follow the same rules as described above.

After considering the safety, tolerability, and PK data in the 300 mg QD (n=9) and initial 400 mg QD (n=7) cohorts, the SRC members agreed to enroll another 6 patients in the 400 mg QD cohort of the dose escalation phase. A total of 13 patients were enrolled in 400 mg QD dose escalation cohorts: Cohort 6 (n=4), Cohort 6+ (n=3), and Cohort 7 (n=6). However, the MTD and RP2D were declared at 300 mg QD on 30 November 2018, when 2 of 6 DLT-evaluable patients reported DLTs in Cohort 7 (400 mg QD) of the dose escalation phase (see subheading d. below for additional information).

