5.1.2 Dose Expansion Phase

The expansion phase will evaluate the anti-cancer activity of surufatinib, and confirm the safety and tolerability of surufatinib at the RP2D determined at the end of the dose escalation phase.

Under amendment 7 of this protocol, the MTD was declared when 2 of the 6 DLT evaluable patients in Cohort 7 (400 mg QD dose) of the dose escalation phase reported DLTs. There was an ad hoc meeting of the SRC on 30 November 2018. The SRC agreed with the declaration of 300 mg QD as the MTD of surufatinib in this trial and agreed that 300 mg QD is the RP2D going forward. The minutes of this ad hoc SRC meeting were distributed to all investigative sites on the same day. It was also agreed that patients who were already receiving 400 mg QD could remain on this dose, provided that 1) there was no major toxicity and 2) the affected patients gave informed consent not to reduce the dose to 300 mg after discussion with the investigator. However, no patients could have their dose escalated to 400 mg going forward, including all patients in the dose expansion phase.

The safety of all enrolled patients will be closely monitored from the time of the initial dose of investigational treatment until 30 days after the last treatment dose. Any SAEs that occur after the informed consent form (ICF) is signed, but before the first dose of study drug is taken, should also be reported. All AEs will be graded in accordance with the NCI CTCAE v. 4.03. Tumor assessments will be conducted according to RECIST Version 1.1 criteria at screening, Cycle 2 Day 1 and every 8 (± 1) weeks thereafter. Confirmation of

CR and PR is required at no less than 4-week intervals between the date of initial response/progression and the confirmation assessment date.

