10.2 Analysis Populations

The following analysis populations have been defined for the study:

- Note: the **DLT Evaluable Set** (dose escalation phase) is defined in [Section 5.1.1](#).
- **Safety Analysis Set (SAS) – (All Treated Population):** This population includes all patients who have received at least one dose of surufatinib. Safety data will be evaluated based on this population's outcome. Patients in the SAS will be analyzed by their actual dose initially received. If patients have dose reduction during the study, all data will be summarized/analyzed based on the initial dose of

study drug received. Efficacy endpoints PFS and OS (OS applies to BTC and STS cohorts only) will be analyzed based on this population.

- **Pharmacokinetic Analysis Set (PKAS):** This population will include all patients who received at least one dose of surufatinib and have at least one PK sample obtained and analyzed.
- **Efficacy Analysis Set (EAS):** This population includes all patients who have received at least 1 dose of surufatinib and have had at least 1 post- baseline tumor assessment. All efficacy endpoints will be analyzed will based on this analysis set, except for PFS and OS, which will be analyzed based on SAS.

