10.5 Pharmacokinetic Analysis

All patients whose plasma samples are collected for analysis of the plasma surufatinib concentration and derivation of PK parameters will be included in the Pharmacokinetic Analysis Set (PKAS).

A non-compartmental model analysis will be performed for plasma concentration data by central lab using WinNonlin (enterprise version). The following statistic data will also be reported: mean value, standard deviation, median value, minimum value, maximum value, geometric mean value, and geometric mean coefficient of variation.

The individual and mean pharmacokinetic parameters determined following analysis of the surufatinib concentration versus time data, will include, but not be limited to total plasma exposure (AUC_{0-∞}), C_{max}, CL/F, and V_z/F. The t_{1/2} will also be estimated. Mean, standard deviation (SD) and coefficient of variation (CV) will be presented. The actual times of plasma sample collection will be used in the determination of the pharmacokinetic parameters.

The methods for calculating pharmacokinetic parameters of surufatinib:

- C_{max}: the maximum observed plasma concentration over the sampling period, taken directly from the data.
- T_{max}: time at which C_{max} occurred, taken directly from the data.
- K_{el}: the first-order rate constant associated with the negative slope of the terminal portion of the log-linear concentration-time curve. A minimum of three points will be used.
- Area under the plasma concentration versus time curve (AUC) to be determined by the linear trapezoidal rule, where AUC_{last} is the AUC from time zero until the last concentration point and AUC_{0-∞} is the AUC_{last} + last concentration point divided by K_{el}.
- Half-life (t_{1/2}) to be determined according to t_{1/2} = 0.693/K_{el} where possible.
- CL/F: systemic clearance to be determined according to Dose/AUC_∞
- V_z/F: apparent volume of distribution, determined according to CL/F/K_{el}
- Dose Proportionality: to be evaluated by investigating the linearity of the relationship between AUC and dose, and C_{max} and dose.
- Accumulation ratio: AUC_{Day15}/AUC_{Day1} or AUC_{Day29}/AUC_{Day1}

Where the concentration data are missing, or listed as less than Lower Limit of Quantification, they will be regarded as zero (0) if occurring before C_{max}. After C_{max}, zero points will not be included in calculations.

Individual and mean surufatinib concentrations will be plotted by dose level.

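### Dose proportionality is listed only for the single-dose expansion phase and is judged by linearity, which is not the same as proportionality

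*Protocol*

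**What the plan says.** **Where the endpoint sits.** Protocol 4.2.4, the synopsis and SAP 3.2.2 put "dose proportionality between AUC and dose and" the same relation for Cmax among the expansion-phase secondary endpoints. The escalation lists (Protocol 4.1.4, SAP 3.1.2) give nine PK parameters, the last being "Accumulation index based on AUC", and do not mention dose proportionality.

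**Doses and sampling.** The expansion objective (4.2.1) covers the BTC, pNET and epNET cohorts at the RP2D and "patients with STS treated at a dose of 300 mg QD", and its note gives the RP2D as 300 mg QD. Section 5.1.2 adds that "no patients could have their dose escalated to 400 mg going forward, including all patients in the dose expansion phase". Table 11 schedules PK samples on Cycle 1 Days 1, 2, 15 and 16. Escalation (5.1.1) planned five levels from 50 to 400 mg.

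**Method.** Protocol 10.5 states: "Dose Proportionality: to be evaluated by investigating the linearity of the relationship between AUC and dose", and likewise for Cmax. It names no model, intercept condition, interval or threshold. The PK analysis set in 10.2 covers both phases: "This population will include all patients who received at least one dose of surufatinib and have at least one PK sample obtained and analyzed". SAP section 2 leaves PK to a separate plan.

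**Formulation.** The new capsule "was introduced while the dose escalation phase of the study was ongoing" (5.1.1) and serves for the rest of the trial. Formulation by dose level is not given.

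**The concern.** Proportionality concerns how exposure changes across doses, so it needs a range of doses. The plan attaches it to the phase with one starting dose and leaves it off the list for the phase with five. A report that followed the endpoint lists literally would have nothing to estimate.

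The method in 10.5 adds a second weakness. Proportionality means that AUC divided by dose is constant. Linearity allows any intercept, so data can be perfectly linear while exposure per mg changes severalfold.

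The question is open for this drug. In rats, Protocol 2.2.2 reports that "The oral bioavailability was observed to be dose dependent": 9.9% at 10 mg/kg and above 50% at the higher doses, possibly because of P-gp efflux. In dogs, the same section reports dose-proportional exposure over 5 to 20 mg/kg. At stake is the description of human PK that later studies would draw on. No dose decision in this trial depends on it.

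**Working it through.** The plan states no power, precision or numerical criterion for this endpoint, so there is no figure to reproduce. The checks use the power model ln(AUC) = a + b x ln(dose), where b = 1 means proportional.

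**1. Expansion alone.** Every starting dose is 300 mg, so ln(dose) is constant, its sum of squares is zero and b has no estimate (design rank 1 of 2). Dose reductions before Day 15 could put a few patients on a lower dose, but toxicity would select them and they would not replace a dose range. Section 10.5 mentions a Day 29 AUC for the accumulation ratio. Table 11 has no such sample, and it would not supply a planned range of doses either.

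**2. Escalation.** Section 5.1.1 gives 35 patients, with 9 at 300 mg and 4 + 3 + 6 = 13 at 400 mg. That leaves 35 - 9 - 13 = 13 for 50, 100 and 200 mg. The split is not stated, so I assume 3/3/7, 3/4/6 or 4/4/5, with no intermediate level. The slope is then estimable. The 90% CI half-width is 1.69 x SD / sqrt(Sxx), where Sxx is the sum of squares of ln(dose), between 13.75 (3/3/7) and 16.80 (4/4/5):

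| Assumed SD of ln(AUC) | 90% half-width for b |
|---|---|
| 0.3 | 0.12 to 0.14 |
| 0.5 | 0.21 to 0.23 |
| 0.7 | 0.29 to 0.32 |

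**3. Linear but not proportional.** Take AUC = 10 x (dose - 30) in arbitrary units.

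| Dose (mg) | 50 | 100 | 200 | 300 | 400 |
|---|---|---|---|---|---|
| AUC | 200 | 700 | 1700 | 2700 | 3700 |
| AUC per mg | 4.0 | 7.0 | 8.5 | 9.0 | 9.25 |

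R-squared on the raw scale is 1.00. AUC per mg rises 9.25 / 4.0 = 2.3-fold. The log-log slope over the five doses is Sxy / Sxx = 3.958 / 2.855 = 1.39. A positive intercept fails the other way: AUC = 200 + 4 x dose is also a perfect line, but AUC per mg falls from 8.0 to 4.5 and the slope is 0.72.

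**4. Formulation.** Suppose the drug is truly proportional, and the new capsule multiplies exposure by F and was given to everyone at 400 mg and to k of the 9 at 300 mg. A fit without a formulation term has expected slope 1 + ln(F) x Sxf / Sxx, where Sxf is the cross-product of ln(dose) with the new-capsule indicator. For the 3/3/7 split with k = 6, Sxf / Sxx = 7.96 / 13.75 = 0.579. With ln(1.25) = 0.223 the slope is 1 + 0.223 x 0.579 = 1.13, and with F = 0.8 it is 0.87. Across the three splits and k = 0, 4, 6, 9, the slope is 0.86 to 0.90 for F = 0.8 and 1.10 to 1.14 for F = 1.25.

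With a formulation term, b stays estimable in every scenario (rank 3 of 3). Its variance rises 1.6- to 3.6-fold, and the half-width at SD 0.5 becomes 0.27 to 0.40.

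**The case against.** **The planned analysis may already use the escalation doses.** The PK set covers both phases, and 10.5 plots concentrations by dose level and is not limited to expansion. This stands. A reader might infer from the endpoint's placement that the plan cannot show proportionality at all. The documents do not support that, because the slope is estimable once escalation data are used. What remains is that the endpoint lists say otherwise and nothing states that the phases are pooled.

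**Gross departures would be visible anyway.** Section 10.5 reports CL/F, which is dose over AUC, and escalation summaries are by dose level. In the first example above, CL/F would fall 2.3-fold from 50 to 400 mg. That example is also artificial, since it gives zero exposure at 30 mg. And 10.5 sets no pass mark, in a study with no formal hypothesis testing. All of this stands and limits the harm. It does not make linearity the right description of proportionality.

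**Confounding with formulation is not documented.** A reader might infer that formulation and dose are confounded. The documents show only that the capsule changed during escalation, with quality attributes described as comparable. The Amendment 3 entry in the history allows a 300 mg start on the new capsule, which suggests possible overlap at that dose and at most partial confounding. The allocations and exposure ratios in step 4 are assumptions, and the resulting shift is smaller than the 90% half-width of 0.21 to 0.23 at SD 0.5.

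**The separate PK plan may name a model, an interval or a formulation term.** It may, and it is not among the documents. It would not correct the endpoint lists or the wording of 10.5.

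**Conclusion.** The point holds, at minor severity. Two parts rest on the documents and simple algebra alone: the endpoint is listed only for the phase that cannot estimate it, and 10.5 describes it by a property that does not imply proportionality. The example's slope of 1.39 shows how far a perfect line can depart from 1. It does not predict surufatinib's PK.

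The formulation part is weaker. Bias is possible but not shown, and the range of 0.86 to 1.14 depends on the assumed allocation and on exposure ratios of 0.8 to 1.25. The precision figures depend on the assumed split of 13 patients and the assumed SDs.

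Severity is minor because this is a descriptive secondary endpoint and 300 mg QD was declared as MTD and RP2D before the current protocol version.

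**What to change.** 1. List dose proportionality for AUC and Cmax under the escalation phase (Protocol 4.1.4, SAP 3.1.2), or state in the synopsis, 4.2.4 and SAP 3.2.2 that escalation and expansion PK are pooled for it.
2. In Protocol 10.5 and the PK plan, replace the linearity criterion with the power model ln(AUC or Cmax) = a + b x ln(dose), and report b with its 90% CI for Day 1 and Day 15.
3. State which formulation each escalation dose level received. Add a sensitivity analysis with a formulation term, or one restricted to the new formulation.

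The cost is a text change and a few regressions on data already collected. The formulation term widens the CI for b materially (slope variance about 1.6 to 3.6 times under the assumed allocations), so it belongs in the sensitivity analysis and not in the main model. If the PK plan already specifies such a model, only the endpoint lists and the wording of 10.5 need to be brought into line with it.

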4.2.5 Exploratory Objectives

- To assess selected tumor markers based on type of malignancy
- To evaluate the OS in patients with advanced BTC and advanced STS

4.2.6 Exploratory Endpoints

- Tumor markers may include, but are not be limited to, serum CEA and CA 19-9 (patients with BTC) serum chromogranin A (CgA) and neuron-specific enolase (NSE) for patients with pNET and epNET; and VEGF for the BTC, pNET, and epNET disease cohorts. Assessment of tumor markers will be performed within 28 days prior to the start of treatment with study drug (C1D1) and at each tumor assessment visit.
- Overall survival limited to patients enrolled to the BTC and STS cohorts only.

5 INVESTIGATIONAL PLAN

5.1 Description of the Study

This is an open-label trial of surufatinib taken orally once daily (QD), and it consists of two phases: a dose escalation phase in patients with advanced solid tumors of any type, and a dose expansion phase in patients with advanced BTC (Arm A), advanced pNETs (Arm B), advanced epNETs (Arm C), or STSs (Arm D). The two phases will be conducted as described below.

5.1.1 Dose Escalation Phase

A 3+3 design will be used for this phase of the study. As of Amendment 7, a total of 35 evaluable patients have been enrolled in the dose escalation phase and the MTD/RP2D has been declared at 300 mg QD.

The trial was to evaluate 5 dose levels of surufatinib 50 mg, 100 mg, 200 mg, 300 mg and 400 mg on a QD dosing schedule.

A minimum of 3 patients were to be enrolled and observed for toxicity at each dose level. If the 3 patients initially enrolled in a dose cohort completed the DLT assessment window (Cycle 1, Days 1-28) without experiencing a DLT, another 3 patients were to be enrolled at the next higher dose level. If 1 of the initial 3 patients enrolled at any dose level experienced a DLT during the DLT assessment window, additional patients were to be enrolled at that dose level for a minimum of 6 evaluable patients for the DLT evaluation. If 1 DLT was observed in 1 of the 6 evaluable patients at this dose level, dose escalation was to proceed to the next pre-defined dose level. If 2 or more DLTs were observed in the 6 evaluable patients at a given dose level, the dose escalation was to be halted. If this dose level was $\geq 50\%$ higher than the previous dose level, an intermediate dose level was to be evaluated for toxicity in the same manner as described above. If the dose level was $< 50\%$ higher than the previous dose level, additional patients were to be enrolled at the previous dose level, if necessary, to form a dose cohort of minimum 6 evaluable patients. The MTD is the highest dose reached with no more than 1 DLT among 6 evaluable patients.

Pharmacokinetic samples will be collected as specified in [Table 12](#).

Safety monitoring and evaluation for dose escalation will be carried out by the Safety Review Committee (SRC) upon completion of the DLT observation period of each cohort. Dose escalation decisions are based on safety and PK data from this ongoing trial, as well as consideration of safety and PK data at comparable drug exposures from patients in previously conducted clinical trials in China.

If a patient meets any DLT non-evaluable criteria during the DLT assessment period, the patient will be replaced.

Patients who complete the DLT observation window (Cycle 1, Day 1-28) and are deemed, in the investigator's judgment, to have benefited from surufatinib treatment could be permitted, at the investigator's discretion, to continue with surufatinib treatment until disease progression, death, intolerable toxicity, pregnancy, or loss of benefit from the study drug. Patients with acceptable toxicity and ongoing clinical benefit were to be permitted to receive surufatinib for up to 1 year at the investigator's discretion and with the sponsor's agreement. Intra-patient dose escalation to a higher dose that has been cleared (ie, no DLT

in 3 patients or 1 or less DLT in at least 6 patients) was to be allowed if the sponsor and investigator both agreed.

Please see the flowchart for dose escalation in Table 3 and [Section 7.2](#) for dose modification instructions.

Table 3 Flowchart of Dose Escalation

Cohort	Dose	Patients	DLTs/patients	Dose Escalation Decision
1	50 mg QD	3-6	0/3	Escalate to 100 mg QD
			1/3	Enroll 3 additional patients
			1/3+0/3	Escalate to 100 mg QD
			1/3+1/3 or 2/3 or 3/3	Stop dose escalation
2 (or 3, 4, etc.)	100 mg QD or higher	3-6 per cohort	Follow the same rules as above	

An improved surufatinib formulation in 50 mg and 200 mg capsules (formulation No. PD-012-042) was introduced while the dose escalation phase of the study was ongoing. The improved surufatinib capsules have replaced the older surufatinib capsules (formulation No. PD-012-023), and will be used for the rest of the trial. Improved formulation (PD-012-042) showed improved consistency of production capability compared to the prior formulation (PD-012-023), including content uniformity with comparable quality attributes. The dose escalation of the new surufatinib capsules will follow the same rules as described above.

After considering the safety, tolerability, and PK data in the 300 mg QD (n=9) and initial 400 mg QD (n=7) cohorts, the SRC members agreed to enroll another 6 patients in the 400 mg QD cohort of the dose escalation phase. A total of 13 patients were enrolled in 400 mg QD dose escalation cohorts: Cohort 6 (n=4), Cohort 6+ (n=3), and Cohort 7 (n=6). However, the MTD and RP2D were declared at 300 mg QD on 30 November 2018, when 2 of 6 DLT-evaluable patients reported DLTs in Cohort 7 (400 mg QD) of the dose escalation phase (see subheading d. below for additional information).

